Following screening and randomization, participants completed self-report measures for the baseline assessment through a secure REDCap link emailed to them. In this trial, we aimed to evaluate changes in primary symptoms as well as to examine secondary and exploratory outcomes, including treatment feasibility and acceptability (e.g., retention and reasons for treatment refusal and dropout, expectancy, and motivation), and changes in depression, functional impairment, delusionality, and quality of life. Therapeutic progress will be broadly assessed with measures of beliefs, behaviors, mood, functioning, and quality of life before, during, and after treatment.

Study Visits and Procedures

Phone Screen: Phone screen procedures were as described above.

Screening Calls and Randomization Procedures: Procedures were as described above.

Assessments: Participants in both conditions were assessed at regular intervals: at baseline (week 0), mid-treatment (week 6), end-of-treatment (week 12), and a 3-month follow-up visit (for details, see Table 1 below). Masters or doctoral-level study IEs conducted clinician-rated assessments, and participants completed self-report questionnaires on the computer via REDCap, a secure data capture system. Please see the schedule of assessments and measures administered (relevant to the primary and secondary aims of this trial) at each time point in Table 1. Assessments required approximately 1 hour. These assessment lengths are like those used in other studies in our program and have been well-tolerated by participants. To avoid dropout, participants were paid \$25 for mid-waitlist, end-of-waitlist, mid-treatment, end-of-treatment, 3-month follow up assessments, and 12-month follow-up assessments. Despite our best efforts to retain participants, we expected dropouts. Except for subjects who withdrew consent to participate, all

who were withdrawn or dropped out of the study were asked to complete all scheduled assessments and were provided remuneration for participation in assessments.

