* Participants in CBT condition go directly into follow-up assessments after week 12. Those in waitlist condition complete follow-up assessments after compassionate care.

[~]Only administered in the RCT active treatment group (not waitlist) during the first 12 weeks of the trial.

Measures Descriptions

Diagnostic Measures

Mini International Neuropsychiatric Interview (M.I.N.I.): The M.I.N.I. (Sheehan et al., 1998) is a semi-structured diagnostic assessment of DSM-5 psychiatric illnesses. The M.I.N.I. is efficient, reliable, and well-validated. It was the sole/primary diagnostic evaluation used to assess for psychiatric diagnoses and establish inclusion and exclusion criteria.

Assessment of Body Image and Related Symptoms

Yale Brown Obsessive Compulsive Scale Modified for BDD (BDD-YBOCS) : This gold-standard 12-item semi-structured clinician-administered scale rates past-week BDD symptom severity (Phillips et al., 1997). It will be the study's primary outcome measure. The BDD-YBOCS has excellent internal consistency ($\alpha=.80$), interrater and test-retest reliability (ICC for total score=.99 and .88, respectively), convergent validity ($r=.55$ with the CGI), and sensitivity to change (Phillips et al., 1997).

BDD-Symptom Scale (BDD-SS): The PI developed the BDD-SS to rate the severity of specific BDD symptoms (Wilhelm et al., 2016). It will be used in the present study to obtain a broader assessment of participants' BDD symptoms and associated thoughts, feelings, and behaviors.

Clinical Global Impression – Improvement Scale (CGI-I) and severity scale (CGI-S): This rating scale, which ranges from 1 (very much improved) to 7 (very much worse), is commonly used in clinical trials (Guy, 1976). Participants completed a CGI for BDD symptoms (CGI-BDD) and the IEs completed a CGI for BDD symptoms (CGI-BDD) and overall symptoms (CGI-global). The CGI was a secondary outcome measure and was also used to determine clinical deterioration of BDD (see Minimizing Risks, below). The CGI also has a severity scale (CGI-S) which was rated by the IE at baseline. The CGI-S determines the patient's level of severity, in comparison to others the IE (clinician) has treated or assessed with the same diagnosis.

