feel that life is empty or wonder if it's worth living"; 2: I think of suicide or death several times a week for several minutes"; and 3: "I think of suicide or death several times a day in some detail, or I have made specific plans for suicide or have actually tried to take my life". Scores on the QIDS-SR were used to evaluate eligibility at the screening visit, and to measure self-reported depressive symptoms at subsequent assessment visits. The QIDS-SR i12 was delivered weekly to participants via the app (in the active group) or via REDCap (in the waitlist group) to monitor for risk concerns during the trial. Scores >0 triggered a popup message to the participant about calling 911/going to the ER, and participants were provided information about contacting a suicide hotline. Scores >1 also triggered a text message alert to the coach with the specific item response given by the participant (i.e., 2 vs. 3). Study clinicians followed up with the participant within 24 hours by phone to assess for risk, and to refer to a higher level of care if clinically indicated (see Minimizing Risks, below). After an initial alert for a participant, study clinicians used clinical judgement when determining follow-up for additional alerts.

Columbia-Suicide Severity Rating Scale (C-SSRS): The C-SSRS (Posner et al., 2011) is a gold-standard, clinician-administered assessment of suicidal ideation and suicide behaviors. The baseline version, which assesses both lifetime and recent time frames, was used to establish eligibility at the baseline/screening visit. The "Update" version, which assesses suicide risk since the last assessment, was used at subsequent study administrations.

Body Parts of Concern List: This list names a wide range of body parts that are the most common areas of appearance concerns for BDD patients. The measure asks participants to indicate which body parts they are preoccupied with.

Assessment of Functioning and Quality of Life

Sheehan Disability Scale (SDS): The SDS uses a Likert scale from 0 (not at all) to 10 (extremely) to assess impairment in occupational, social, and family domains. It has strong internal consistency and validity (Sheehan et al., 1996).

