In-App Coach Training and Qualifications: BA-level coaches were study staff members with a Bachelor of Arts (BA) or Bachelor of Science (BS) degree in Psychology or a related field. Based on preliminary findings from our feasibility and acceptability trial, we anticipated that the coaches' involvement would be light-touch and focus mostly on motivation and problem-solving, as needed, whereas the app itself would be the primary mode of treatment delivery. Specifically, in our pilot trial the coach spent less than 2.5 minutes per patient per week on average responding to chat messages. Research on technology-based treatments likewise suggests that coaches primarily serve to motivate patients and increase accountability and adherence. Coaches received training before assisting in treatment as a coach (e.g., completing the MGH Psychiatry Academy CBT training course for BDD) and were required to pass (>90% correct) the MGH Psychiatry Academy BDD knowledge test. To ensure ongoing high-quality treatment, study staff members who were licensed clinicians with expertise in CBT for BDD provided weekly supervision to coaches, with additional supervision as needed if questions arose.

IE Training and Qualifications, and Procedures to Ensure Assessment Integrity and Interrater Reliability

Assessments were conducted by independent evaluators (IE) who had Masters or Doctoral-level degree in clinical psychology or related mental health fields and who were employed at MGH. The IEs were otherwise uninvolved in study procedures. Training and reliability checks were done to ensure that IEs conducted ratings in a uniform way. Raters first received instruction in the SCID-I/P, MINI, SCID-II, BDD-YBOCS, BABS, and CGI from [name] or another gold-standard expert rater, prior to beginning as an IE. The IEs were then supervised twice monthly by the PI. The IE were required to demonstrate reliability on the BDD-YBOCS and BABS at a criterion of .80 ICC, compared to measures rated by [name] or another gold-standard rater. All assessments were audiotaped for reliability ratings. Names were not included on digital recordings. To reduce rater drift, a trained reliability rater meeting the same qualifications as the IE reviewed 15% of randomly selected audiotaped interviews at regular intervals. IEs were blind to randomized conditions.

Privacy and Confidentiality

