Participants' clinical improvement or deterioration was assessed weekly via a participant-rated CGI-BDD collected via the app (or REDCap, in waitlist condition). Participants could be withdrawn from the study if their clinical condition deteriorated substantially. Deterioration was defined by a combination of (1) a rating of 6 (much worse) or 7 (very much worse) on the weekly, participant-rated CGI-BDD across 2 subsequent weeks and (2) PI judgment that remaining in the study was not in the participant's best interest. Of note, a single rating of 6 or 7 on the weekly, participant-rated BDD-CGI also triggered a notification to the clinician/coach via text message and email. In the case that a BA-level coach was notified that a participant's CGI indicates deterioration, they notified a doctoral-level clinician as soon as possible (and within 24 hours). A study clinician then followed up with a phone evaluation within 24 hours of the alert and referred the participant to a higher level of care if clinically indicated. After an initial alert for a participant, study clinicians could use clinical judgement when determining follow-up for additional alerts.

5. Ratings on the QIDS-SR item 12 (suicide item) were carefully monitored weekly via the app (or REDCap, in waitlist condition); a score >0 at any assessment triggered a pop up message to be presented to the patient within the mobile app reminding participants that if they were experiencing suicidal thoughts, they should seek professional help or go to the emergency room right away. Links to 911, as well as a national suicide hotline, were provided within this popup notification. A score >1 also triggered notification to the clinician/coach via text message or email. In the case that a BA-level coach was notified that a participant reported a score >1 , they notified a doctoral-level study clinician as soon as possible (and within 24 hours). A study clinician, PI, or independent evaluator then followed up with a phone evaluation within 24 hours of the alert and referred the participant to a higher level of care if clinically indicated. After an

initial alert for a participant, study clinicians could use clinical judgement when determining follow-up for additional alerts.

6. Participants could also be withdrawn if, in the judgment of the PI, remaining in the study posed a substantial risk to the participant or a higher level of care is needed.

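### The suicide-item alert rule lets an independent evaluator phone randomised participants, which can reveal the arm to a rater of the primary endpoint and conflicts with the evaluators' stated blind and non-involvement

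*Combined protocol and SAP*

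**What the plan says.** Five places in the combined protocol and SAP bear on this.

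- **Section VII.D, Minimizing of Risks and Safety Reporting, item 5.** After a weekly QIDS-SR item 12 score above 1: "A study clinician, PI, or independent evaluator then followed up with a phone evaluation within 24 hours of the alert".
- **Section V, Measures Descriptions, QIDS-SR.** On delivery: "The QIDS-SR i12 was delivered weekly to participants via the app (in the active group) or via REDCap (in the waitlist group". On the same alert: "Scores >1 also triggered a text message alert to the coach with the specific item response given by the participant", and then "Study clinicians followed up with the participant within 24 hours by phone to assess for risk". No IE is named here.
- **Section V, IE Training and Qualifications.** "The IEs were otherwise uninvolved in study procedures". The same paragraph ends: "IEs were blind to randomized conditions".
- **Section V, Assessments and BDD-YBOCS entry.** "Masters or doctoral-level study IEs conducted clinician-rated assessments". The primary outcome is one of these: "This gold-standard 12-item semi-structured clinician-administered scale rates past-week BDD symptom severity". The BABS, a secondary outcome, is also a clinician interview.
- **Section V, Treatment Condition Questionnaire.** At week 12 the IE records which arm they believe the participant was in, and how confident they are.

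The weekly CGI-BDD deterioration alert, described just before item 5, gives its follow-up call to a study clinician only.

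**The concern.** Participants in an app-versus-waitlist trial know their own arm. For interview-rated outcomes, the main protection against rating bias is therefore an evaluator who does not know it. Item 5 gives that evaluator a second task after randomisation: a risk call to a participant who may talk freely about using the app or waiting for it. The answer that triggers the call also arrives by a different route in each arm. No section hides the route from the caller, and none keeps an IE who made the call from later rating that participant.

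At stake are the week 12 BDD-YBOCS contrast and the BABS comparison. Any loss of blinding would fall on participants who reported suicidal ideation during the trial, not on a random subset.

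**Working it through.** **1. The plan's own sample size (Section VI.D).** Inputs: two-sided alpha 0.05, power 0.90, equal allocation, 15% dropout, effect size 0.90 lowered to 0.81. A two-sample comparison of means (noncentral t) gives:

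- d = 0.90: 27 per arm; 27/0.85 = 31.8, so 32 per arm and 64 in total.
- d = 0.81: 34 per arm; 34/0.85 = 40 per arm and 80 in total.

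Both match the plan. The point does not depend on them; they supply the 34 per arm used in step 3.

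**2. The passages side by side.**

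| Question | Item 5 | Rest of the document |
|---|---|---|
| Who may call after an item 12 alert? | Study clinician, PI or IE | Study clinicians (QIDS-SR entry) |
| Who calls after a weekly CGI-BDD alert? | Not covered | Study clinician |
| Do IEs do anything besides assess? | Yes, if they take the call | No (IE section) |
| Can the call fall between randomisation and week 12? | Yes, the item is weekly | Yes, both arms receive it during the trial |
| May the calling IE rate the participant later? | Not addressed | Not addressed |

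An IE who takes such a call is doing something other than outcome assessment, which contradicts the stated non-involvement. It puts the blind at risk, because the participant knows the arm and the answers come by app or REDCap according to arm. The Treatment Condition Questionnaire measures loss of blinding at week 12 but does not prevent it. The IE call in item 1 belongs to screening, before randomisation, and is not affected.

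**3. Illustration of size.** The documents give neither how often an IE took a call nor how far knowledge of the arm moves a rating. Assume that a share f of one arm is rated by an unblinded IE, with a bias of b SD in one direction. Then

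shift in contrast = f × b; noncentrality = f × b × √(34/2) = f × b × 4.123; 66 degrees of freedom.

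| f | b | Shift (SD) | Shift/0.81 | Two-sided rejection rate, no true effect |
|---|---|---|---|---|
| 0.05 | 0.25 | 0.0125 | 1.5% | 5.03% |
| 0.05 | 0.50 | 0.025 | 3.1% | 5.12% |
| 0.10 | 0.25 | 0.025 | 3.1% | 5.12% |
| 0.10 | 0.50 | 0.05 | 6.2% | 5.47% |
| 0.20 | 0.25 | 0.05 | 6.2% | 5.47% |
| 0.20 | 0.50 | 0.10 | 12.3% | 6.91% |

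This uses a simple comparison of week 12 means in place of the planned mixed model, so it shows order of magnitude only.

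**The case against.** **The text permits; it does not report.** The IE is one of three possible callers. No section says that an IE made such a call, learned the arm, or later rated that participant. This stands. A reader might infer that the rule reveals the arm and so broke the blind; the documents support only that it can.

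**The coach cue is weak.** A coach is assigned on starting the app, so an alert relayed by a coach might seem to mark the app arm. But item 5 sends alerts to the clinician or coach under a rule covering both arms, and the coach then tells a doctoral-level clinician, not the IE. This stands, and nothing here rests on that cue. Nor do the documents show arm information reaching IEs through the PI's supervision.

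**Some calls cannot matter.** Item 12 is also weekly after waitlist participants cross over, when the week 12 contrast is complete. True, but the item is equally weekly before week 12.

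**The QIDS-SR entry is only a summary.** It points forward to the risk section and omits the PI as well. That softens the mismatch over callers. It does not touch the conflict with the IE section.

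**Leaks can happen anyway.** IEs interview everyone at weeks 6 and 12, using forms on adverse events, concomitant treatment and life events, and no section asks participants to conceal their arm. That is a general gap. An unscripted risk call adds to it, by an amount that cannot be separated out from the documents. Second review of 15% of taped interviews checks rater drift, not knowledge of the arm.

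**Larger figures are tempting.** Assuming 30% of participants affected and 0.6 SD gives 0.30 × 0.6 = 0.18 SD, which is 22% of 0.81, and an error rate of 11.5% (normal approximation, SE √(2/34) = 0.243). But if the three roles shared calls equally and the same IE always rated, 30% would need 0.30 × 3 = 90% of participants to trigger an alert, in a trial that excludes C-SSRS ideation scores of 2 or more and QIDS-SR totals of 21 or more at entry. That end of the range is not credible.

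**Conclusion.** The point holds as a contradiction in procedure and a missing safeguard. Item 5 allows an IE to make risk calls between randomisation and week 12. This conflicts with the IE section, differs from the QIDS-SR entry, and can disclose the arm to someone who may then rate the primary BDD-YBOCS and the BABS.

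The effect on the primary result is probably small. On the assumed values above, the shift is 0.0125 to 0.10 SD and the two-sided error rate about 5.0% to 6.9%. This rests on 34 completers per arm, bias confined to one arm, and an effect on the mean only. If both arms were affected, the shifts would add or cancel according to their signs. A reader might take it that the bias favours the app; that is a plausible expectation, but the documents do not establish direction.

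**What to change.** Leave the safety call and its timing unchanged. Reconcile item 5, the QIDS-SR entry and the IE section on who makes it.

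Add one sentence to item 5 and one to the IE section: an IE who takes part in an alert call for a randomised participant before week 12 does not do that participant's later week 6 or week 12 ratings where another trained IE is available, and each such call is logged. The qualification is needed because the documents do not say how many IEs there were.

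The procedures are written largely in the past tense, so the ratings may already be complete. In that case, report by arm how many participants were rated by an IE who had taken their call, and repeat the primary analysis without those ratings as a sensitivity analysis. The affected participants keep their other assessments in the mixed model. Because the removed ratings come from people who triggered an alert, read the result as a check and not as a replacement.

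The cost is a few sentences, a log, some rater scheduling and one small extra analysis.

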3-month Follow-up Feedback to Technologists: Participants could choose to meet with technologists from Koa Health (sponsor) via a Partners-approved, secure, HIPAA-compliant clinical video platform (Healthcare secure Zoom) at the 3-month follow-up, for the technology experts to obtain input and feedback on the usability and feasibility of the CBT app. This meeting would take approximately 1.5 hours, and participants would be reimbursed \$25 for completion of the 3-month follow-up feedback visit with technologists.

Table 1: Measures table

Measure	RANDOMIZED CONTROL TRIAL: ARM 1								COMPASSIONATE CARE (WAITLIST CONDITION CROSSES TO APP)			
	Baseline	Baseline Re-assess	Weekly	Week 4	Mid-Treatment Assess (wk 6)	Post-Treatment Assess (wk 12) †	3-month Follow-up*	12-month Follow-up*	Weekly	Week 4	Mid-Treatment Assess (wk 6)	Post-Treatment Assess (wk 12)
Treatment History Checklist	✓											
Treatment History Medication	✓											
Treatment History Psychosocial	✓											
AE Form		✓			✓	✓	✓	✓			✓	✓
Body Parts of Concern Checklist (BPCC)	✓											
BDD Y-BOCS	✓	✓			✓	✓	✓	✓			✓	✓
BABS	✓	✓			✓	✓	✓	✓			✓	✓
MINI	✓											
C-SSRS Lifetime	✓											
C-SSRS Update		✓				†						
CGI-C	✓	✓			✓	✓	✓	✓			✓	✓
Treatment Condition Questionnaire						✓						
CONCOM Form		✓			✓	✓	✓	✓			✓	✓
BDD-PSR	✓	✓			✓	✓	✓	✓			✓	✓
Life Events Question		✓			✓	✓	✓	✓			✓	✓
Technologist Interview Notes						✓						
PHQ-2			✓						✓			
QIDS-SR – Q12			✓						✓			

CGI-P		✓	✓		✓	✓	✓	✓	✓	✓	✓	✓
Demographics	✓											
Lifetime Psychiatric Medications	✓											
Credibility Expectancy Rating [~]	✓				✓	†				✓		
QIDS-SR	✓	✓			✓	✓	✓	✓		✓		✓
QLESQ	✓				✓	✓	✓	✓		✓		✓
SDS	✓				✓	✓	✓	✓		✓		✓
CSQ [~]					✓	✓				✓		✓
Treatment Utilization Questionnaire [~]					✓	✓	✓			✓		✓
App Feedback Questionnaire (Endpoint) [~]						✓						✓
App Feedback Questionnaire (Baseline) [~]	✓					†						
App Feedback Questionnaire (Midpoint) [~]					✓					✓		

If more than ten days elapse between a patient's initial baseline screening assessment and the start of treatment, the study IE would re-administer the AE form, AE log, BDD-YBOCS, BABS, CONCOM form, CMED log, and CThERAPY log to that participant, and they would complete an additional CGI-P (see "Baseline Re-Assess," above).

† Post-treatment assessment also functions as the baseline assessment for those in waitlist condition, who cross over into compassionate care. † indicates supplemental measures added only for compassionate care baseline.

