7. Treatment through app-based CBT was supplemented with electronic communication with a study coach, who could answer questions and guide participants through the treatment as needed. See *In-App Coach Training and Qualifications*, above, for details.
8. The independent evaluator(s) were highly experienced, highly trained, and closely supervised.
9. [name] (the PI) was available, if necessary, to discuss the study, alternative treatments, or any concerns about the study with participants if requested by the participant, coaches, or raters.
10. The PI and her co-investigator and the participants' study coach were available to answer study questions via the app or phone. This was clearly communicated orally and in writing to study participants.
11. All participants were provided with referral resources.
12. The study coaches and raters (IEs) made every attempt to help participants feel comfortable when discussing sensitive material. Participants could skip questions on assessments that they were uncomfortable answering.
13. If exposure exercises suggested through the treatment app were too anxiety provoking, participants were able to do alternative exercises that caused less anxiety.
14. The CBT treatment initially emphasized cognitive restructuring, which we anticipated would be less anxiety provoking than exposure treatment alone and would make exposure more tolerable.
15. Technologists from Koa Health who conducted the technology feedback interviews were trained professional staff with experience conducting patient interviews. They received additional training (including a multi-day workshop) from our team (MGH OCD and Related Disorders Program) on CBT and issues of confidentiality. They completed CITI training.
16. Three clinical psychologists or researchers familiar with BDD were selected to serve as a Data Safety Monitoring Board, to review the study once a year.
17. Participants designated a relative or friend who could be contacted should the subject be unavailable and the investigator had concerns about the subject's well-being.

We anticipated that the above procedures would be effective in protecting study participants against potential risks.

Adverse event reporting:

See below: "Adverse event reporting guidelines"

E. Radiation risks

Not applicable

VIII. POTENTIAL BENEFITS

A. Potential benefits to participating individuals

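### As written, a skipped weekly suicide item (QIDS-SR item 12) is handled like a score of 0, unless the app or REDCap forces an answer, which the protocol does not say

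*Combined protocol and SAP*

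**What the plan says.** Three parts of the combined protocol and SAP bear on this.

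- **Permission to skip.** Section VII.D, Minimizing of Risks and Safety Reporting, list item 12: "Participants could skip questions on assessments that they were uncomfortable answering". No measure is exempted.
- **Triggers on the weekly suicide item.** List item 5 of the same section: "a score >0 at any assessment triggered a pop up message to be presented to the patient within the mobile app", and "A score >1 also triggered notification to the clinician/coach via text message or email". A clinician, the PI or an evaluator then telephones within 24 hours. After a participant's first alert, follow-up of later ones is left to clinical judgement. Section V, Measures Descriptions (QIDS-SR), gives the same thresholds: "Scores >1 also triggered a text message alert to the coach with the specific item response given by the participant". The item goes out weekly, by app in the active arm and by REDCap in the waitlist arm.
- **Weekly answers that do not reach staff.** Section VII.C recognises that a device fault of this kind could delay a safety response, and offers phone contact as mitigation. It does not mention an item left blank by the participant.

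Sections VI and IX.D describe regular checks of data completeness, with no timing and no clinical action attached.

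**The concern.** A person who does not want to answer a question about suicide may be a person staff would want to hear from. The protocol itself describes BDD as carrying raised suicide risk (background section) and says that suicidal ideation may increase during the study (Section VII.D). Table 1 lists three weekly measures: PHQ-2, QIDS-SR item 12 and the participant-rated CGI. Only item 12 asks about suicide. If that item can be passed over and a blank sets nothing in motion, declining to answer looks to the alert system the same as reporting no thoughts of suicide or death. What is at stake is the speed of a safety response, not the estimate of treatment effect.

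**Working it through.** The plan gives no figure to reproduce. The check is to apply the written rules to every possible input and then look for any rule on a blank.

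**Step 1: the trigger rules.** Inputs: the item's four response choices, 0 to 3 (Section V, QIDS-SR); pop-up if score > 0; staff alert if score > 1 (Section V and list item 5).

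| Response to item 12 | Pop-up (> 0) | Staff alert (> 1) |
|---|---|---|
| 0 | no | no |
| 1 | yes | no |
| 2 | yes | yes |
| 3 | yes | yes |
| blank | condition not met | condition not met |

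The pop-up follows 3 of the 4 answers and the alert 2 of the 4. A blank meets neither condition and shares its row of outcomes with 0. The alert is also described as carrying the response given, which presupposes that there is one.

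**Step 2: does the permission to skip reach the weekly item?** No sentence says so outright. Three points favour it. Section V cites Table 1 as the schedule of assessments, and Table 1 has a weekly column. Section VII.C uses the term assessments for weekly symptom measures. List item 5 speaks of an item 12 score at any assessment. Against it, the preceding sentence in list item 12 is about coaches and raters discussing sensitive material, and the Assessments paragraph of Section V names only the scheduled visits. The broader reading is plausible but inferred.

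**Step 3: is there a rule for a blank?** None was found. Nothing makes the item mandatory, treats a blank as a positive screen, or calls for contact after one. The mitigation in Section VII.C is confined to device faults. The completeness checks in Sections VI and IX.D are not linked to the 24-hour follow-up. The documents do not say whether the app or REDCap required an answer.

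**Step 4: what still operates when item 12 is blank?**

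- Independent evaluators assess both arms at weeks 6 and 12, with an adverse event form each time (Section V, Table 1).
- In the app arm, coaches exchange messages with participants and can arrange phone check-ins (Section V, Treatment Format).
- The weekly CGI-BDD has its own alert: "a single rating of 6 or 7 on the weekly, participant-rated BDD-CGI also triggered a notification". It rates change in BDD rather than suicidality, and it too needs a rating.
- The PI may withdraw a participant judged to be at substantial risk (list item 6).
- Active suicidal ideation and severe depression are excluded at entry (Section III). Crisis information is in the app, and each participant names a contact person (list items 3, 4 and 17).

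None of these is prompted by a blank, but none needs an item 12 score either.

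**The case against.** The strongest reply is that the deciding fact lies outside the documents. Required-field settings would plausibly sit in the REDCap data dictionary or the app specification. If the item was required, there is no gap, and silence about a form setting is not in itself an error. The permission to skip also reads most naturally in an interview setting. Both points stand as limits: the finding concerns the written rules, and no failure in conduct is shown. They do not remove it. The protocol specifies the triggers in detail and grants a general permission to skip, yet never says how the two meet.

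A second reply is that the remedy is partial. A reluctant participant can enter 0, a wholly missed weekly form also produces no alert, and flagging a refusal sits uneasily with the right to refuse. This is fair. It is the reason to leave the follow-up to clinical judgement rather than make it automatic.

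A reader might go further and infer from the ticks in Table 1 that no clinician-rated suicide scale was scheduled once app treatment began. The documents do not support building on that. Section V says of the C-SSRS Update that it is the version "which assesses suicide risk since the last assessment, was used at subsequent study administrations". The tick positions are also doubtful: in the crossover block, the midpoint app questionnaire appears under week 4 rather than week 6. Any conflict between text and table over the C-SSRS would be a separate question and is not used here.

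**Conclusion.** The point holds in a limited form. Under the written rules a skipped item 12 produces the same response as a score of 0, namely none. This rests on two assumptions: that the general permission to skip covers the weekly item, and that the software did not force an answer. The first is plausible on the protocol's own usage; the second cannot be settled from the documents.

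No frequency can be given, because no skip rate is reported. The consequence is modest, since several human safeguards work independently of the item. A reader might infer that participants at risk went unmonitored, or that harm followed; nothing in the documents shows either. The weekly item is a monitoring measure rather than an analysed endpoint, so the primary and secondary analyses are untouched. This is an inexpensive safety improvement.

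**What to change.** In list item 5 of Section VII.D, state that QIDS-SR item 12 is a required field with a *prefer not to answer* choice. This should apply in the app and in REDCap, and in both weekly phases of Table 1: the randomised 12 weeks and the waitlist crossover. Have that choice show the same crisis links as the pop-up and flag the coach or clinician, with follow-up by clinical judgement. Cross-refer to this in list item 12 so that the right not to answer is plainly kept. If the software already forced an answer, one sentence saying so would settle the point.

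The cost is one field setting and one response option in each system, one sentence in list item 5 and a cross-reference. The downside is some extra clinician contacts, whose number cannot be estimated without a skip rate. A weekly form left wholly undone is not covered and would need its own rule.
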